| Data analysis | 
Primary endpoint The overall response rate at 3 months of study treatment along with the corresponding exact 90% confidence interval will be provided. The primary analysis will be performed on the FAS.
 
Key Secondary endpoint The response rate at 3 months of study treatment along with the corresponding exact 95% confidence interval will be provided by dose level at randomization study treatment.
 
Sample size calculation The planned sample size of 30 is determined based on the accuracy of estimated overall response rate at the end of 3 months. Under these assumptions, the sample size of 30 can demonstrate that the lower limit of the exact two-sided 90% CI for the overall response rate is not less than the clinically required minimum response rate.
 |
| Key words | Pasireotide, acromegaly, Phase II |

1 Background

1.1 Overview of acromegaly and pituitary gigantism pathogenesis, epidemiology and current treatment

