10.4.2 Statistical hypothesis, model, and method of analysis

The total-group response rate at 3 months of study treatment along with the corresponding Clopper-Pearson exact two-sided 90% confidence interval will be provided. The primary analysis will be performed on the FAS.

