10.4.4 Supportive analyses

The primary analysis will also be repeated on the PPS.

As subgroup analysis, the primary analysis will also be repeated by prior medication (i.e., somatostatine analogue and dopamine agonist) (yes or no) on the FAS if the number of patients in the subgroup is large enough.

The total-group response rate at 3 months of study treatment along with the corresponding Clopper-Pearson exact 95% confidence interval will be provided on the FAS and PPS.

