10.8 Sample size calculation

The planned sample size of 30 is determined based on the accuracy of estimated total-group response rate at the end of 3 months.

The response rate is the proportion of responders, where responders are defined as patients with the reduction of mean GH levels to $< 2.5 \mu\text{g/L}$ and normalization of IGF-1. The response rates at 20 mg, 40mg and 60mg in [CSOM230C2110] were comparable (30% at 20mg, 41.7% at 40mg, and 38.5% at 60mg). Furthermore, the dose of pasireotide LAR will be adjusted according to efficacy and safety. It is considered, therefore, that the efficacy of pasireotide LAR can be evaluated more appropriately based on the response rate of all groups combined. In this study, based on the results from CSOM230C2110, the expected total-group response rate will be at least 30%.

In [CSOM230C2305], patients inadequately controlled with 12 month octreotide LAR study treatment were crossed over to pasireotide LAR. The response rate at 3 months after crossover was 17.3% (two-sided 95% CI: [9.8%, 27.3%]). Since a large number of patients who enroll to this study are assumed to be inadequately controlled with octreotide LAR treatment, a clinically meaningful minimum response rate is set as 10% based on the lower limit of two-sided 95% CI, 9.8%.

The expected drop out rate is 10% based on [CSOM230C2305]. The patients with missing values of mean GH levels or IGF-1 at the assessment at 3 months of study treatment or who discontinue prior to the assessment at 3 months of study treatment will be considered as non-responders.

Under these assumptions, the expected total-group response rate adjusted by the expected drop out rate is 27%. The sample size of 30 can demonstrate that the lower limit of the Clopper-Pearson exact two-sided 90% CI for the total-group response rate is not less than the clinically meaningful response rate, 10%.

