5.9 Efficacy evaluation

5.9.1 Primary analysis

Primary variable

The primary variable is the total-group response rate defined as the proportion of patients with the reduction of mean GH levels to $< 2.5 \mu g/L$ and the normalization of IGF-1 at 3 months of study treatment. This has already been reported in [the 12 month CSR].

Please see the Section 4.1.9 about how to handle missing values and discontinuations.

Primary analysis

The total-group response rate at 3 months of study treatment along with the corresponding Clopper-Pearson exact two-sided 90% confidence interval was reported in [the 12 months CSR] and not applicable in this document.

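### Does the primary analysis need to state a comparison with the 10% minimum response rate used to size the trial?

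*Protocol*

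**What the plan says.** Protocol 10.8 opens with a precision rationale: "The planned sample size of 30 is determined based on the accuracy of estimated total-group response rate at the end of 3 months". It then says that "a clinically meaningful minimum response rate is set as 10" per cent, taken from the lower 95% limit (9.8%) of the 3-month response rate in patients who crossed over from octreotide LAR in the phase III study. It also says that "the expected total-group response rate will be at least 30" per cent, and reduces this to 27% for 10% dropout counted as non-response. It concludes: "The sample size of 30 can demonstrate that the lower limit of the Clopper-Pearson exact two-sided 90% CI for the total-group response rate" is no lower than 10%. SAP 7 repeats the argument. The synopsis gives no number and uses firmer language: the lower limit "is not less than the clinically required minimum response rate".

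The analysis text is shorter. Under a heading that includes the word hypothesis, Protocol 10.4.2 says: "The total-group response rate at 3 months of study treatment along with the corresponding Clopper-Pearson exact two-sided 90% confidence interval will be provided". The analysis set is the FAS. Under Supportive analyses, Protocol 10.4.4 adds that the "corresponding Clopper-Pearson exact 95% confidence interval will be provided on the FAS and PPS". SAP 5.9.1 records that the rate "along with the corresponding Clopper-Pearson exact two-sided 90% confidence interval was reported in" the 12-month CSR and is not part of the final analysis. None of these three sections mentions 10%.

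**The concern.** A single-arm response rate has no comparator, so the benchmark gives it meaning. Here the benchmark sits in the sizing text and is absent from the analysis text. If 10% is a criterion, a lower limit below it means that the minimum was not shown, and a limit at or above it means that it was. If 10% was only a planning figure, neither statement is made and the interval stands alone.

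Three features sharpen this. The synopsis wording suggests a requirement. Two intervals are planned for the same rate on the same FAS, and at one particular count they fall on opposite sides of 10%. The supplied SAP was written after the primary result had been reported, so an unstated reading could in principle be chosen to suit the result.

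**Working it through.** **Inputs.** Planned n = 30, expected rate 30%, dropout 10% counted as non-response, floor 10% and crossover rate 17.3% (Protocol 10.8, SAP 7). Primary interval: exact two-sided 90% on the FAS (10.4.2). FAS: all randomized (10.1.1). Number randomized: 33 (Amendment 3 rationale, SAP 2).

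**1. Reproduce the plan's own statement.** Adjusted rate: 0.30 × 0.90 = 0.27. Expected count: 0.27 × 30 = 8.1, so 8. The Clopper-Pearson lower limit is the α/2 quantile of Beta(x, n − x + 1), with α = 0.10. For 8 of 30 the 90% interval is 14.0% to 43.0%. The lower limit exceeds 10%, so the statement in 10.8 holds at the expected count. It claims no power.

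**2. Find the count on which the comparison turns.** Lower limits:

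| Responders | 90% limit | 95% limit |
|---|---|---|
| 6 of 30 | 9.09% | 7.71% |
| 7 of 30 | 11.50% | 9.93% |
| 8 of 30 | 14.02% | 12.28% |
| 6 of 33 | 8.23% | 6.98% |
| 7 of 33 | 10.40% | 8.98% |
| 8 of 33 | 12.68% | 11.09% |

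With the primary 90% interval, 7 responders are needed at either size. With the 95% interval, 8 would be needed.

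**3. Find the chance of reaching 7.** Binomial P(X ≥ 7):

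| True rate (dropouts as non-responders) | n = 30 | n = 33 |
|---|---|---|
| 17.3% | 25% | 34% |
| 27% | 74% | 83% |
| 30% | 84% | 91% |

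The chance of 6 or fewer at 27% is therefore 26% for 30 patients and 17% for 33. Neither is a ceiling. At 17.3% it is 75% and 66%, and 10.8 itself expects many enrolled patients to resemble the crossover group. For the reported result, the n = 33 column applies.

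**4. Size the 90%/95% split.** The two lower limits straddle 10% only at exactly 7 responders. At 27% that has probability 15% for n = 30 and 12.5% for n = 33.

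**5. Set the sections side by side.**

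- Endpoint: total-group response at 3 months in 10.4.1, 10.4.2, 10.8, SAP 5.9.1 and SAP 7.
- Interval: exact two-sided 90% in 10.4.2, 10.8, SAP 5.9.1 and SAP 7.
- Role of the 95% interval: supportive, by its placement in 10.4.4.
- Interval attached to 10%: the 90% one, in 10.8 and SAP 7.

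Nothing conflicts. The only thing missing is a pointer from the analysis sections to 10.8.

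**The case for a change.** The strongest case for acting is that the benchmark should be tied explicitly to the primary result because that result was known when this SAP was written. At the protocol's own adjusted rate there is a 26% chance with 30 patients of falling short, which the words of 10.8 do not convey. A few sentences would close the question at almost no cost.

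Part of this stands. The supplied analysis sections do not repeat the comparison, and the text does not say in so many words whether 10% is a criterion. The status also matters in both directions: at 7 or more responders, only the criterion reading supports saying that the minimum was shown.

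The rest is weaker. The floor, the interval and the endpoint are all written in 10.8, and no amendment lists a change to that section, so there is little room to pick a convenient reading later. The choice between the 90% and 95% intervals is settled by the labels primary and supportive. An estimation design in phase II need not state a hypothesis, and 10.8 presents the sample size as a matter of accuracy. A rule and a probability inserted into the final-CSR SAP would be added after the result, in a document that does not perform the analysis.

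**Conclusion.** No change to the protocol or SAP is warranted. This is a missing cross-reference that an analyst or reader fills from 10.8. It is not a contradiction, and no figure is wrong. Following the plan as written gives a correct rate and a correct 90% interval, and the lower limit can be set against the documented 10% directly. The dividing line is 7 responders: 10.4% for 7 of 33, against 8.2% for 6 of 33. Adding the comparison to the plan would change no estimate, interval or analysis set. A CSR may usefully say on which side of 10% the 90% lower limit falls, with the 95% interval as supportive, but the plan does not depend on it.

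This rests on three assumptions. All 33 randomized patients are in the FAS; SAP 4.3 would remove anyone without prior written consent. The probabilities treat patients as independent with one common response rate. And the finding that the analysis text omits 10% covers only the supplied protocol and the final-CSR SAP. The plan for the month-3 and month-12 analyses and the 12-month CSR are not supplied and may already state the comparison.

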10.9 Power for analysis of key secondary variables

Not applicable.

11 Ethical considerations and administrative procedures

11.1 Regulatory and ethical compliance

This clinical study was designed, shall be implemented and reported in accordance with the ICH Harmonized Tripartite Guidelines for Good Clinical Practice, with applicable local regulations (including European Directive 2001/20/EC and US Code of Federal Regulations Title 21), and with the ethical principles laid down in the Declaration of Helsinki.

11.2 Responsibilities of the investigator and IRB/IEC/REB

The protocol and the proposed informed consent form must be reviewed and approved by a properly constituted Institutional Review Board/Independent Ethics Committee/Research Ethics Board (IRB/IEC/REB) before study start. Documentation (written and dated approval or favorable opinion) that the protocol and informed consent have been approved by the IRB/IEC/REB must be given to Novartis before study initiation. Prior to study start, the investigator is required to sign a protocol signature page confirming his/her agreement to conduct the study in accordance with these documents and all of the instructions and procedures found in this protocol and to give access to all relevant data and records to Novartis monitors, auditors, Novartis Clinical Quality Assurance representatives, designated agents of Novartis, IRBs/IECs/REBs and regulatory authorities as required.

11.3 Informed consent procedures

Eligible patients may only be included in the study after providing written (witnessed, where required by law or regulation), IRB/IEC/REB-approved informed consent or, if incapable of doing so, after such consent has been provided by a legally acceptable representative of the patient. In cases where the patient's representative gives consent, the patient should be informed about the study to the extent possible given his/her understanding. If the patient is capable of doing so, he/she should indicate assent by personally signing and dating the written informed consent document or a separate assent form. Informed consent must be obtained before conducting any study-specific procedures (i.e. all of the procedures described in the protocol). The process of obtaining informed consent should be documented in the patient source documents. The date when a subject's Informed Consent was actually obtained will be captured in their eCRFs.

Novartis will provide to investigators, in a separate document, a proposed informed consent form (ICF) that is considered appropriate for this study and complies with the ICH GCP guideline and regulatory requirements. Any changes to this ICF suggested by the investigator must be agreed to by Novartis before submission to the IRB/IEC/REB, and a copy of the approved version must be provided to the Novartis monitor after IRB/IEC/REB approval.

Women of child bearing potential should be informed that taking the study medication may involve unknown risks to the fetus if pregnancy were to occur during the study and agree that in order to participate in the study they must adhere to the contraception requirement for the duration of the study. If there is any question that the patient will not reliably comply, they should not be entered in the study.

Additional consent form

Not applicable.

11.4 Discontinuation of the study

Novartis reserves the right to discontinue this study under the conditions specified in the clinical study agreement. Specific conditions for terminating the study are outlined in [Section 4.4](#).

11.5 Publication of study protocol and results

Novartis assures that the key design elements of this protocol will be posted in a publicly accessible database such as clinicaltrials.gov. In addition, upon study completion and finalization of the study report the results of this study will be either submitted for publication and/or posted in a publicly accessible database of clinical study results.

11.6 Study documentation, record keeping and retention of documents

Each participating site will maintain appropriate medical and research records for this trial, in compliance with Section 4.9 of the ICH E6 GCP, and regulatory and institutional requirements for the protection of confidentiality of subjects. As part of participating in a Novartis-sponsored study, each site will permit authorized representatives of the sponsor(s) and regulatory agencies to examine (and when required by applicable law, to copy) clinical records for the purposes of quality assurance reviews, audits and evaluation of the study safety and progress.

Source data are all information, original records of clinical findings, observations, or other activities in a clinical trial necessary for the reconstruction and evaluation of the trial. Examples of these original documents and data records include, but are not limited to, hospital records, clinical and office charts, laboratory notes, memoranda, subjects' diaries or evaluation checklists, pharmacy dispensing records, recorded data from automated instruments, copies or transcriptions certified after verification as being accurate and complete, microfiches, photographic negatives, microfilm or magnetic media, x-rays, and subject files and records kept at the pharmacy, at the laboratories, and medico-technical departments involved in the clinical trial.

Data collection is the responsibility of the clinical trial staff at the site under the supervision of the site Principal Investigator. The study case report form (eCRF) is the primary data collection instrument for the study. The investigator should ensure the accuracy, completeness, legibility, and timeliness of the data reported in the eCRFs and all other required reports. Data reported on the eCRF, that are derived from source documents, should be consistent with the source documents or the discrepancies should be explained. All data requested on the eCRF must be recorded. Any missing data must be explained. Any change or correction to a paper eCRF should be dated, initialed, and explained (if necessary) and should not obscure the original entry. For electronic eCRFs an audit trail will be maintained by the system. The investigator should retain records of the changes and corrections to paper eCRFs.

The investigator/institution should maintain the trial documents as specified in Essential Documents for the Conduct of a Clinical Trial (ICH E6 Section 8) and as required by applicable regulations and/or guidelines. The investigator/institution should take measures to prevent accidental or premature destruction of these documents.

Essential documents (written and electronic) should be retained for a period of not less than fifteen (15) years from the completion of the Clinical Trial unless Sponsor provides written permission to dispose of them or, requires their retention for an additional period of time because of applicable laws, regulations and/or guidelines

11.7 Confidentiality of study documents and patient records

The investigator must ensure anonymity of the patients; patients must not be identified by names in any documents submitted to Novartis. Signed informed consent forms and patient enrollment log must be kept strictly confidential to enable patient identification at the site.

11.8 Audits and inspections

Source data/documents must be available to inspections by Novartis or designee or Health Authorities.

11.9 Financial disclosures

Financial disclosures should be provided by study personnel who are directly involved in the treatment or evaluation of patients at the site - prior to study start.

12 Protocol adherence

Investigators ascertain they will apply due diligence to avoid protocol deviations. Under no circumstances should the investigator contact Novartis or its agents, if any, monitoring the study to request approval of a protocol deviation, as no authorized deviations are permitted. If the investigator feels a protocol deviation would improve the conduct of the study this must be considered a protocol amendment, and unless such an amendment is agreed upon by Novartis and approved by the IRB/IEC/REB it cannot be implemented. All significant protocol deviations will be recorded and reported in the CSR.

Appendix 1: Instructions for use

1 Procedure for pasireotide LAR 20 mg dosage strength

For preparation of the microparticle powder suspension for injection, the standard vehicle for microparticles has to be taken to reconstitute the suspension in the 6R vials.

- Take one (1) drug product vial with the following label
Project name: pasireotide LAR
Form: MPVI
Dosage: 20 MG/VIAL
- Remove the transparent flip-off cap from the vial.
- Take one vehicle ampoule and break off the upper part.
- Withdraw the content of the vehicle ampoule with the **18 G (min 50 mm length)** needle and e.g. a 3 ml syringe.
- Remove air bubbles by pushing the piston and adjust the volume to 2 ml.
- Inject 2 ml of vehicle into the vial containing the powder (20mg).
- Shake the vial **up and down** at least 30 seconds in order to get a homogenous suspension.
- Withdraw the whole volume of suspension from the vial with the same **18 G (min 50 mm length)** needle and e.g. a 3 ml syringe.
- Change the needle with a new **20 G** needle for i.m. injection.
- Remove air bubbles by pushing the piston.
- Immediately, inject the whole volume of suspension intra-muscularly to the patient.

2 Procedure for pasireotide LAR 40 mg dosage strength

For preparation of the microparticle powder suspension for injection, the standard vehicle for microparticles has to be taken to reconstitute the suspension in the 6R vials.

- Take one (1) drug product vial with the following label
Project name: pasireotide LAR
Form: MPVI
Dosage: 40 MG/VIAL
- Remove the transparent flip-off cap from the vial.
- Take one vehicle ampoule and break off the upper part.
- Withdraw the content of the vehicle ampoule with **18 G (min 50 mm length)** needle and the e.g. a **3 ml syringe**.
- Remove air bubbles by pushing the piston and adjust the volume to 2 ml.
- Inject 2 ml of vehicle into the vial containing the powder (40 mg).
- Shake the vial **up and down** at least 30 seconds in order to get a homogenous suspension.
- Withdraw the whole volume of suspension from the vial with the same **18 G (min 50 mm length)** needle and the e.g. a **3 ml syringe**.

- Change the needle with a new 20 G needle for i.m. injection
- Remove air bubbles by pushing the piston.
- Immediately, inject the whole volume of suspension intra-muscularly to the patient.

3 Procedure for pasireotide LAR 60 mg dosage strength

For preparation of the microparticle powder suspension for injection, the standard vehicle for microparticles has to be used to reconstitute the suspension in the 6R vials.

- Take one (1) drug product vials with the following label
Project name: pasireotide LAR
Form: MPVI
Dosage: 20 MG/VIAL
- Take one (1) additional drug product vial with the following label
Project name: pasireotide LAR
Form: MPVI
Dosage: 40 MG/VIAL
- Remove the transparent flip-off cap from the vials.
- Take one vehicle ampoule and break off the upper part.
- Withdraw the content of the vehicle ampoule with the **18 G (min 50 mm length)** needle and the 3 ml syringe.
- Remove air bubbles by pushing the piston and adjust the volume to 2 ml.
- Inject 2 ml of vehicle into the first vial containing the powder (20mg).
- Shake the vial **up and down** for 30 seconds in order to get a homogenous suspension.
- Withdraw the whole volume of suspension from the vial with the **18 G (min 50 mm length)** needle and the **3 ml syringe**.
- Inject the whole volume of suspension into the second vial (40mg)
- Shake the vial **up and down** at least 30 seconds in order to get a homogenous suspension.
- Withdraw the whole volume of suspension from the vial with the **18 G (min 50 mm length)** needle and e.g. a **3 ml syringe**.
- Change the needle with a new **20 G** needle i.m. injection
- Remove air bubbles by pushing the piston.
- Immediately, inject the whole volume of suspension intra-muscularly to the patient

Appendix 2: Medications known to be associated with QT interval prolongation

The following list of drugs is generally recognized to have a possible association with QT prolongation. This list is not considered to be all inclusive and any questions regarding the QT prolongation potential should be discussed with the Novartis Medical Monitor.

Drugs that are generally accepted by the QTdrugs.org Advisory Board of the Arizona CERT to have a risk of causing torsade de pointes are listed below.

| Generic Name | Brand Name | Class |
|------------------|-------------|---|
| Bepidil | Vasacor® | Anti-anginal / heart pain |
| Amiodarone | Cordarone® | Anti-arrhythmic / abnormal heart rhythm |
| Amiodarone | Pacerone® | Anti-arrhythmic / abnormal heart rhythm |
| Disopyramide | Norpace® | Anti-arrhythmic / abnormal heart rhythm |
| Dofetilide | Tikosyn® | Anti-arrhythmic / abnormal heart rhythm |
| Ibutilide | Corvert® | Anti-arrhythmic / abnormal heart rhythm |
| Procainamide | Pronestyl® | Anti-arrhythmic / abnormal heart rhythm |
| Procainamide | Procan® | Anti-arrhythmic / abnormal heart rhythm |
| Quinidine | Cardioquin® | Anti-arrhythmic / abnormal heart rhythm |
| Quinidine | Quinaglute® | Anti-arrhythmic / abnormal heart rhythm |
| Sotalol | Betapace® | Anti-arrhythmic / abnormal heart rhythm |
| Clarithromycin | Biaxin® | Antibiotic / bacterial infection |
| Sparfloxacin | Zagam® | Antibiotic / bacterial infection |
| Erythromycin | Erythrocin® | Antibiotic;GI stimulant / bacterial infection; increase GI motility |
| Erythromycin | E.E.S.® | Antibiotic;GI stimulant / bacterial infection; increase GI motility |
| Arsenic trioxide | Trisenox® | Anti-cancer / Leukemia |
| Astemizole | Hismanal® | Antihistamine / Allergic rhinitis |
| Terfenadine | Seldane® | Antihistamine / Allergic rhinitis |
| Pentamidine | Pentam® | Anti-infective / pneumocystis pneumonia |
| Pentamidine | NebuPent® | Anti-infective / pneumocystis pneumonia |
| Probucol | Loelco® | Antilipemic / Hypercholesterolemia |
| Chloroquine | Aralen® | Anti-malarial / malaria infection |
| Halofantrine | Halfan® | Anti-malarial / malaria infection |
| Domperidone | Motilium® | Anti-nausea / nausea |
| Mesoridazine | Serentil® | Anti-psychotic / schizophrenia |
| Thioridazine | Mellaril® | Anti-psychotic / schizophrenia |
| Haloperidol | Haldol® | Anti-psychotic / schizophrenia, agitation |
| Pimozide | Orap® | Anti-psychotic / Tourette's tics |
| Chlorpromazine | Thorazine® | Anti-psychotic/ Anti-emetic / schizophrenia/ nausea |
| Cisapride | Propulsid® | GI stimulant / heartburn |
| Levomethadyl | Orlaam® | Opiate agonist / pain control, narcotic dependence |
| Methadone | Dolophine® | Opiate agonist / pain control, narcotic dependence |
| Methadone | Methadose® | Opiate agonist / pain control, narcotic dependence |
| Droperidol | Inapsine® | Sedative;Anti-nausea / anesthesia adjunct, nausea |

Reference: qt drugs.org/medical-pros/drug-lists/drug-lists.cfm
